Study Protocol

Official title:

**The Precise Surgical Treatment of Chronic Thromboembolic Pulmonary Hypertension:
Pulmonary Endarterectomy Guided by Three-dimensional Pulmonary Angiography**

Brief title

**Pulmonary Endarterectomy Guided by CT Scanning for Patients With Chronic
Thromboembolic Pulmonary Hypertension---PEACT**

Acronym:PEACT

Sponsor:Fuwai Hospital,Chinese Academy of Medical Sciences,Peking Union Medical College

Study types: interventional,Randomized single-blind controlled study

Document Date: 12/19/2018

Abbreviation and acronyms

CTEPH=chronic thromboembolic pulmonary hypertension;PEA=pulmonary endarterectomy;PAP=pulmonary artery pressure;PVR=pulmonary vascular resistance;PTG=precise therapy group;UCG=ultrasonic cardiogram;CPET=cardiac pulmonary exercise test;CT=computed tomography;RHC=right sided heart catheterization;WHO=World Health Organization;NT-pro BNP=N-terminal pro B-type natriuretic peptide.INR=international normalized ratio;6MWD=6 minutes walking distance; mmHg=millimeter mercury column;CF=coagulation factor;UCSD=University of California, San Diego;NOAC=new oral anticoagulant;3-D=Three-dimensional;

Brief Introduction of this study

This study is a randomized single-blinded controlled study to investigate the efficiency of 3-D pulmonary imagings, including 3-D pulmonary angiography and 3-D enhanced computed tomography, patients received PEA surgeries in our center was randomized into 2 groups, the PTG group (group 1) and traditional PEA therapy group (group 2), the peri-operative hemodynamic improvement and peri-operative prognosis such as peri-operative mortality and other severe complications were documented for both groups, and the follow-up result of UCG, CPET and RHC are compared for these 2 groups so as to investigate their long-term result after PEA surgeries. A total of more than 72 cases of patients with CTEPH are expected to be included into this study, with informed consent form signed, a longest 48 months follow-up result will be recorded, and the whole designed study is expected to end at the year 2022.

Catalog

1 Background.....	5
2 Objectives(Focus of the study).....	6
3 Design and Method.....	7
4 Eligibility/intervention information/Arm information.....	10
5 Outcome measures and time frame.....	12
6 Statistical Analysis Plan.....	13
7 Quality Control.....	14
8 Reference.....	15
9 Appendix.....	16
Sample of original medical record(1 patient).....	16

1 Background

CTEPH is an acquired pulmonary hypertension disease with poor prognosis, 5-year mortality rate of the patients without any intervention can be as high as 90%[1]. It is generally believed that pulmonary thrombosis in these patients can be attributed to residual unresolved thrombus in acute pulmonary embolism patients or to the deep vein thrombus in lower extremities[2, 3]. 12000 to 15000 new cases of CTEPH was found every year in the United States[4], for these patients, PEA surgeries was reported as a golden standard therapy with a significantly better survival prognosis and life quality achieved compared with pure medicine therapy or pulmonary balloon angioplasty by many centers[5-7]. However, even in the United States, only 300 cases can received PEA therapies each year, the reasons for this low population received PEA surgeries are as below: 1). PEA is a extremely skill-demanding operation for the cardiac surgeons, it is reported that 1/2 to 1/3 of CTEPH patients are considered inoperable by surgeons in Europe[7]. Half of the reasons considered inoperable was the embolism location considered difficult to be found and removed during the operation[7]; Therefore, accurate positioning and complete removal of the embolism for patients with CTEPH are the key to successful operation. The latest 3-D imaging technology can accurately assess the obstructive severity of each pulmonary segments, Rotating 3-D pulmonary angiography can analyze the location and direction of each pulmonary artery, which can help the surgeons to determine the surgical difficulty of each pulmonary segment for each patient. In summary, PEA surgeries guided with high-definition 3-D imaging techniques might lead to a better hemodynamic result better survival result in the long-term period after surgeries, and might provide a solution to position the embolism before surgeries, so as to more conveniently remove the pulmonary embolism during the surgeries.

2 Objectives(Focus of the study)

- 1) To investigate the importance of the appliance of the 3-D imaging technique for PEA surgeries,especially for patients with peripheral UCSD levels;
- 2) To establish a standard assessing method with high-definition enhanced CT scanning and pulmonary angiography;establish a quantitative scoring method using CT scanning and pulmonary angiography to assess the severity of CTEPH and surgical indications;
- 3) To compare the result between group 1 and group 2,so as to find out the possible benefits in the precise therapy group(group 1);
- 4) To promote the appliance of 3-D imaging techniques for patients with CTEPH, and establish a standard precise PEA strategy guided by enhanced CT scanning and pulmonary angiography,in order to further improve the surgical result for patients with CTEPH,especially for patients with peripheral changes.

3 Design and Method

1) General design

This is a randomized single-blinded controlled study, 72 cases of patients are expected to be enrolled into this study, and randomized into 2 groups. The endpoint of these 2 groups will be compared to determine the efficiency of the appliance of 3-D imaging techniques for PEA procedures.

2) Clinical data collection process:

Pre-operative period: From admission to the moment before surgeries. Basic clinical information including the patients' age, gender, symptoms, clinical diagnosis, WHO classes, disease history et al. Blood test such as the thrombus forming tendency test, blood coagulation function test, coagulation factor activity test and N-terminal B-type natriuretic peptide (NT-proBNP) et al were collected. Other examinations included CT scanning, MRI, CPET, RHC and pulmonary angiography, pulmonary nuclide perfusion imaging, respiratory function test and UCG et al. The major parameters of these examinations are collected.

[figure not shown]
Operation period: The RHC result immediately before and after PEA surgeries are documented, the anesthesia record and CPB record, surgical specimen pathological record, intra-operative cerebral oxygen saturation data will be collected;

Post-operative period before discharge: Pulmonary nuclide perfusion imaging, CT scanning and UCG should be done in this period.

Follow-up period: A routine 3-, 6-, 12-, 24 months follow-up will be done, the follow-up contents include the measuring of NT-pro BNP, UCG, CPET, CT scanning, RHC, pulmonary angiography, pulmonary perfusion imaging, MRI and RHC. Among which the CPET, MRI, RHC and pulmonary angiography should be done after 6 months after surgeries. All the redo examinations could be done in any follow-up period, but at least 1 time of these examinations should be done in the whole follow-up period, and the follow-up time should be recorded.

[figure not shown]
3) CT Imaging assessment:

① According to the imaging examinations before surgeries, the location of each occluded pulmonary segment and their shape were identified and the affected pulmonary segments were divided into 3 types: i) segments that are easy to reach; ii) segments that are hard to reach (seen in the picture below), and severely occluded; iii) segments that are hard to reach but slightly occluded;

[figure not shown]
An example of segments hard to reach. As shown in the picture, the shape of LA5 of this patient is exactly perpendicular to the surgical direction, which lead to a fact that the embolism in this segment very hard to strip. For the subsegment LA8a+b, it is too far away from the proximal artery, which is very hard to reach at surgeries.

② All the occlusion severity of each segment and narrow severity of each segment is assessed with CT scanning;

An example of constructed CT imaging of the pulmonary segment: A demonstration of the anatomic structure of pulmonary segments. White arrow: not severely narrow segment of RA9; Red arrow: severely narrow segment of LA4.

4) Research process:seen in the picture below.

4 Eligibility/intervention information/Arm information

Eligibility:

Patients were **eligible** if they had met all the following conditions:

[figure not shown]
- 1) Diagnosed with CTEPH by pulmonary angiography and RHC examinations;
- 2) The location of the embolism can be reached in surgery;
- 3) Whether or not combined with auto-immune diseases;

Patients were **not eligible** if they had met any one of the following conditions:

- 1) history of other severe diseases and surgical therapy is contraindicated;
- 2) Unwillingness to participate or without informed consent;
- 3) acute pulmonary embolism;
- 4) pulmonary sarcoma;
- 5) Patients with mitral valve diseases, or other conditions that may lead to cardiogenic pulmonary hypertension;
- 6) Pulmonary hypertension caused by pulmonary arteritis.

Intervention information:

Precised analyzed CT scanning and pulmonary angiography will be done for the patients in the precise therapy group, and the patients in Group 1 will receive PEA procedure with the guide of precise 3-D imaging techniques (seen in the picture below)

An example of precise therapy process.A,3-D CT constructed images,which can provide the detailed information of each pulmonary segmental shape and their distribution;B,enhanced CT imaging of pulmonary segment,to assess the occluded severity of each pulmonary segment;C:Diagrammatic sketch of pulmonary artery embolism's location,red marked font refer to pulmonary segments with occupying changes;as shown in the picture,the RA4,RA2,RA5 is completely occluded,other affected segment is partially occluded.D.Surgical specimen;the occupying lesions in each pulmonary segment is stripped according to the embolism location identified by high-resolution CT scanning(seen in picture C);E,clearly opened pulmonary segment entrance after precise stripping therapy.

Arm information:All the patients included into this study met the requirements above and randomized into 2 groups:

group 1:precise PEA therapy with the guide of 3-D imaging techniques;

group 2:traditional PEA therapy solely by surgical probe and traditional CT scanning/pulmonary angiography method.

100 cases of randomized group were generated,which consisted of 50 cases of group 1 and 50 cases of group 2, and 100 cases of randomized number was generated paralleled with the randomized group.According to the date of admission of each patients,they are included into the randomized group one by one,any patient met the criteria of the **not eligible** described above will be excluded from this experiment, and all the patients consent to participate in this study will not know their specific group, the chief surgeon can only know the random grouping situation after the patients been admitted into hospital.

5 Outcome measures and time frame

The primary endpoint for assessment of the efficacy was the peri-operative hemodynamic improvement, peri-operative mortality, major complications after surgery, and deaths in the follow-up period.

Secondary endpoint were the measuring values of NT-pro BNP, parameters of MRI, UCG and CPET in the follow-up period, the CT scoring changes from baseline to follow-up period, and WHO function classes in the follow-up period, as well as disease directly associated cost (average cost) in the follow-up period.

6 Statistical Analysis Plan

This is a prospective randomized single-blinded controlled study, the major endpoint is the hemodynamic improvement after the surgeries.

1) Sample Size:

Sample size estimation was based on a hypothesis that the mean PAP of patients of PTG can be decreased by 8 mmHg more than that of the traditional group. Given the standard deviation of 12 mmHg was expected in the measurement of mean PAP, with a power of 80% and a significance statistically level of 5% on both side, a sample size of 36 of the PTG group was required.

2) Statistical Analysis:

The analysis was based on the principle of “Intention to Treat” (ITT). All randomized patients (regardless of whether they violate the protocol) will be included in the final analysis.

Continuous variables are presented as mean \pm standard deviation, unless otherwise specified. Significant differences were determined with the Mann-Whitney test or independent t-test according to the their distribution, Wilcoxon matched pairs signed rank test or paired t-test for the paired variables. Categorical variables were compared between the 2 groups using the chi-square test or Fisher exact test. Kaplan-Meier method was used to estimate survival, log-rank test was used to evaluate the survival difference between different groups.

The pulmonary occluded severity will be scored using CT scanning and pulmonary angiography for each patients, the scoring result will be compared with the hemodynamic result to investigate their possible correlations using Spearman Correlation Analysis.

All the statistical analysis were performed using SPSS version 22.0. P value less than 0.05 was considered statistically significant.

7 Quality Control

1) Data accuracy:

All the participants in this study are responsible for the data collection process, all the original medical document should be pictured or scanned as the evidence of recorded data; for parameters with possible subjective error, the original imaging or assessment profile should be saved, the parameters estimated by

2) Group coordination

Fuwai hospital was the largest cardiac surgery center in China and also one of the largest center in the world. Up to now, we had established a coordination team of CTEPH in our center, which consist of cardiac surgery department, pulmonary disease center, radiology department, intensive-care unit and ultra-sonic department, nuclear medicine department in our center.

All the imaging data had been evaluated by at least 2 professional staffs in that field, and the CT constructed imaging, pulmonary angiography imaging had been saved for re-assessment in case of possible subjective bias.

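### The clinical follow-up secondary endpoints have no stated analysis time, and their between-arm tests leave out the baseline value and follow-up time that the trial already collects

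*Combined protocol and SAP*

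**What the plan says.** **Timing (section 3, Follow-up period).** The schedule reads "A routine 3-, 6-, 12-, 24 months follow-up will be done". A minimum time is set for some examinations: "Among which the CPET, MRI, RHC and pulmonary angiography should be done after 6 months after surgeries". The next sentence relaxes the timing: "All the redo examinations could be done in any follow-up period, but at least 1 time of these examinations should be done". It ends by asking for the timing to be kept: "and the follow-up time should be recorded". The Brief Introduction adds "a longest 48 months follow-up result will be recorded" and "the whole designed study is expected to end at the year 2022".

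**Purpose (Brief Introduction).** "the follow-up result of UCG, CPET and RHC are compared for these 2 groups so as to investigate their long-term result".

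**Endpoints (section 5).** NT-proBNP, MRI, UCG and CPET parameters, WHO class and disease-related cost are placed in follow-up without a visit. The CT score is a change from baseline to follow-up, also without a visit.

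**Baseline (section 3, Pre-operative period).** "Other examinations included CT scanning, MRI, CPET, RHC and pulmonary angiography". NT-proBNP, UCG and WHO class are collected there as well.

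**Tests (section 6).** Between arms: independent t-test or Mann-Whitney for continuous variables, chi-square or Fisher for categorical ones. Paired tests are listed for paired variables. Kaplan-Meier and log-rank are listed for survival.

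**The concern.** Three things are missing from the visible text for the six clinical follow-up endpoints.

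- **A time.** Nothing says at which visit the arms are compared.
- **A value rule.** Nothing says whether the first, last, closest or average value counts when a patient has several.
- **Use of data in hand.** The between-arm tests contain no term for baseline (only the CT score uses it, as a change) and none for months since surgery, although both are collected.

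The flexible-timing sentence has two readings. On the broad one it covers every repeat examination, so a single UCG at 3 months would satisfy section 3 and could still enter what the introduction calls a long-term comparison. On the narrow one it covers only CPET, MRI, RHC and angiography. Those still have no upper time limit, and UCG, NT-proBNP and CT would be due at four visits, which makes the missing value rule matter more. The minimum-time sentence and the flexible-timing sentence stand next to each other and need to be reconciled.

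At stake are the precision and the meaning of the secondary comparisons.

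**Working it through.** **Inputs from the documents.** Difference 8 mmHg, SD 12 mmHg, two-sided 5%, power 80%, 36 in the precise therapy group and 72 in total (sections 3 and 6); visits at 3, 6, 12 and 24 months (section 3).

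**Assumptions.** The documents give no effect, drift over time or correlation for the follow-up endpoints. The effect of 8/12 = 0.667 SD is borrowed from the sample size calculation. Drift and correlation are varied.

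**1. The plan's own figure.** n = 2 × (1.960 + 0.842)² × (12/8)² = 35.3, so 36 per arm. It reproduces. Exact t-test power at 36 per arm is 79.7%.

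**2. Unadjusted test, timing balanced.** Suppose half of each arm is measured early and half late, and the outcome drifts by d SD in between. The variance becomes 1 + 0.25d². Noncentral t, 70 df, type I error 5%:

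| d (SD) | Variance | Power |
|---|---|---|
| 0 | 1.000 | 79.7% |
| 0.3 | 1.0225 | 78.8% |
| 0.5 | 1.0625 | 77.2% |
| 0.8 | 1.160 | 73.6% |

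**3. Model with arm, baseline and months.** If the months term removes the drift, the residual SD is √(1 − r²), where r is the correlation of baseline with follow-up. The noncentrality is 0.667 / (residual SD × √(2/36)), with 68 df.

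| r | Residual SD | Power, 36 per arm | Power, 30 per arm |
|---|---|---|---|
| 0.3 | 0.954 | 83.2% | 75.8% |
| 0.5 | 0.866 | 89.6% | 83.4% |
| 0.7 | 0.714 | 97.4% | 94.4% |

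The unadjusted power at 30 per arm, without drift, is 71.9%.

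**4. Where the gain comes from.** Take d = 0.5 and balanced timing. With baseline alone, the residual variance is 1 − r² + 0.0625. The figures with months come from simulation, with a linear months term fitted to a drift that levels off.

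| r | t-test | Baseline only | Baseline and months | Added by months |
|---|---|---|---|---|
| 0.3 | 77.2% | 80.7% | 81.9% | 1.2 points |
| 0.5 | 77.2% | 87.2% | 88.9% | 1.7 points |
| 0.7 | 77.2% | 95.8% | 97.0% | 1.2 points |

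With r = 0 the adjusted model gives 79.6%, so months alone buy little.

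**5. What time the effect refers to.** Assume the true effect rises linearly from 0.3 SD at 6 months to 0.7 SD at 24. It is then 0.333 at 7.5 months, 0.433 at 12 and 0.700 at 24. With one value per patient, the average effect depends on the shares examined at those three times:

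- 60/30/10: 0.6 × 0.333 + 0.3 × 0.433 + 0.1 × 0.700 = 0.40
- equal thirds: (0.333 + 0.433 + 0.700) / 3 = 0.49
- 10/30/60: 0.1 × 0.333 + 0.3 × 0.433 + 0.6 × 0.700 = 0.58

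In simulation (20,000 trials per setting, 36 per arm) the t-test averaged 0.399, 0.488 and 0.583. The model with arm, baseline and months averaged 0.398, 0.488 and 0.585, so it does not remove this dependence. Adding arm × (months − 12) gave 0.434, 0.433 and 0.433 at 12 months.

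**6. Open choice of value, upper bound.** If the smallest p-value across visits were taken, type I error would be 7.0 to 9.1% with two visits (12 and 24 months) and 9.3 to 15.7% with four, for within-patient correlation 0.9 down to 0.5. The four-visit case includes 3 months, so it cannot apply to CPET or MRI under the after-6-months rule.

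**The case against.** **The plan names visits, and once is only a minimum.** A visit-by-visit comparison is a natural reading. This stands: a reader might infer that the plan pools values from mixed times, but it never says so. What remains is that no visit is chosen for the comparison.

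**Figures not shown may hold a schedule.** One follows the follow-up paragraph, one is the research-process picture, and one follows the patient-coordination text in section 7. This also stands, and it is why the point is limited to the visible text. A schedule of visits would not put baseline or months into the tests.

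**The harm is small.** With balanced timing there is no bias, and power falls by only 0.9 to 2.5 points for a drift of 0.3 to 0.5 SD. A reader might infer that the comparisons are biased. That needs timing to differ by arm, and nothing in the documents shows that it does. For scale only: with d = 0.5 SD and a 20-point difference between arms in the share examined late, the bias is 0.5 × 0.2 = 0.1 SD and the false-positive rate about 7.0%. Nor does anything suggest that the sponsor would choose the most favourable value.

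**Not every between-arm test ignores time.** Correct. Log-rank uses it for survival, so the point covers only the tests of these secondary endpoints.

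**Time adjustment gets credit that belongs to baseline.** This stands, as steps 4 and 5 show. Omitting baseline is a loss of efficiency, not an error.

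**Conclusion.** The point holds as a cheap improvement, not as a flaw that invalidates an analysis. For NT-proBNP, MRI, UCG, CPET, CT score and WHO class, the visible plan states no analysis time or value rule, and its tests leave collected information unused.

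- **Efficiency.** Power is about 83/90/97% with the adjusted model, against 79.7% unadjusted without drift. Almost all of the difference is due to baseline; months add 1 to 2 points at a drift of 0.5 SD.
- **Meaning.** If the effect changes with time, the estimate follows the booking pattern (0.40 to 0.58 SD in the example).
- **Choice of value.** It stays open until a rule is written. The error rates in step 6 are a ceiling, not a forecast.

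Every size rests on assumed effect, drift and correlation values. The peri-operative haemodynamic comparison, the 36 per arm and the survival analysis are untouched. Follow-up RHC is mentioned in the introduction but is not listed among the secondary endpoints in section 5.

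**What to change.** Write the following into sections 5 and 6 before analysis.

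1. **Main comparison.** For each of the six endpoints, fit a model with arm, baseline value and recorded months since surgery, using every examined patient. Use the log scale for NT-proBNP if it is skewed and an ordinal model for WHO class.
2. **Reference time.** Name one existing visit after 6 months, for example 12 months, and count for each patient the value closest to it. Do not discard values outside a window. If the study closes at the end of 2022, patients operated on up to December 2021 can reach 12 months.
3. **Sensitivity estimate.** Add arm × (months − 12) and report the arm effect at 12 months, because the main model still averages over booked times if the effect changes.
4. **Reporting.** Give by arm the timing of examinations, deaths before the reference visit and missing examinations. Adjusting for months does not remove bias from deaths or from outcome-related timing.
5. **Cost endpoint.** Give follow-up cost its own rule, for example cost over a fixed period or per month of follow-up. The closest-value rule and baseline adjustment do not suit it.

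If a figure not shown already fixes the analysis visit, cite it in sections 5 and 6; the adjusted model still applies.

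**Cost.** Some wording and a little more analysis. Baseline values and follow-up time are already collected, and no visit or patient is added. The downsides are reliance on a modelled time trend and a less precise estimate at the reference time: simulated power 77/85/95% for item 3 against 82/89/97% for item 1, at baseline correlation 0.3/0.5/0.7.

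### Segments are typed before surgery as easy or hard to reach, but no endpoint uses the type and the CT-score change has no baseline adjustment, so a gain mainly in hard-to-reach segments may be diluted

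*Combined protocol and SAP*

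**What the plan says.** Section 3, item 3 (CT Imaging assessment) records the data segment by segment. From the pre-operative imaging, "the affected pulmonary segments were divided into 3 types: i) segments that are easy to reach; ii) segments that are hard to reach" and severely occluded; the third type is "iii) segments that are hard to reach but slightly occluded". Severity is also graded by segment: "All the occlusion severity of each segment and narrow severity of each segment is assessed with CT scanning".

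The rationale in Section 1 is segmental too: rotating 3-D angiography shows where each artery lies, "which can help the surgeons to determine the surgical difficulty of each pulmonary segment for each patient". Objectives 1 and 4 in Section 2 single out peripheral disease.

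Section 5 does not carry the typing forward. The primary endpoint is haemodynamic and clinical: "The primary endpoint for assessment of the efficacy was the peri-operative hemodynamic improvement, peri-operative mortality, major complications after surgery", and deaths in follow-up. The only listed outcome that reflects clearance of the arteries is a secondary one, "the CT scoring changes from baseline to follow-up period".

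Section 6 adds that "The pulmonary occluded severity will be scored using CT scanning and pulmonary angiography for each patients", and the one analysis written specifically for the score is a correlation: "the scoring result will be compared with the hemodynamic result to investigate their possible correlations using Spearman Correlation Analysis". A comparison between arms would fall under the general rule for continuous variables (independent t-test or Mann-Whitney test), which has no baseline covariate.

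**The concern.** The plan creates the variable closest to its own mechanism and then leaves it out of the analysis. Two separate losses can follow.

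- **Dilution.** If the conventional operation already clears easy segments well, those segments show little difference between arms. Averaging them with hard segments shrinks the difference.
- **Extent of disease.** A raw change in a summed score is large in a patient with many affected segments and small in a patient with few, whatever the surgery achieved. With no baseline adjustment, this variation enters as noise.

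At stake is the interpretation of the one listed outcome that could show directly whether guidance clears what would otherwise be left behind. The issue is how the outcome is built in all patients. It is not a patient subgroup comparison.

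**Working it through.** **1. The plan's own figure.** Section 6 sizes the trial on mean PAP: difference 8 mmHg, SD 12 mmHg, 80% power, two-sided 5%. Then n per arm = 2 × (1.960 + 0.842)² × 12² / 8² = 2 × 7.85 × 2.25 = 35.3, rounded up to 36. This reproduces the stated 36 (72 in total, Section 3). Power at 36 per arm is 80.7% by the normal approximation and 79.7% by the t distribution. The sample size is not in question.

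**2. Inputs the documents do not give.** There is no score formula, no share of hard segments, no clearance rate and no SD for the score. Everything below rests on assumptions.

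**3. Dilution of the estimate.** Let h be the share of hard segments, and Δh and Δe the differences between arms in hard and easy clearance. The difference in overall percent cleared is h × Δh + (1 − h) × Δe.

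- Δe = 0, Δh = 20 points: 4 points at h = 0.2, 8 at h = 0.4, 12 at h = 0.6, 16 at h = 0.8.
- Δe = 10, Δh = 20, h = 0.4: 0.4 × 20 + 0.6 × 10 = 14 points.
- Δe = 10, Δh = 10: 10 points at any h, so no dilution.

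**4. Power with no effect in easy segments.** Simulation with 36 per arm, 4 to 20 affected segments per patient (mean 12), easy clearance 90% in both arms, hard clearance 60% v 40%, between-patient SD 0.5 on the logit scale unless stated, and Welch t-test. Each segment is counted as cleared or not.

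| Setting | Raw change | % of all cleared | % of hard cleared |
|---|---|---|---|
| 25% hard | 11% | 23% | 54% |
| 40% hard | 18% | 47% | 76% |
| 50% hard | 28% | 59% | 82% |
| 40% hard, SD 1.0 | 14% | 27% | 55% |

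Type I error was 4–6% throughout. Separately coded versions of the 40% setting gave 15–16%, 51–52% and 78–79%. A different model (hard 70% v 50%, easy 95% in both arms, within-patient correlation 0.1) gave 24%, 57% and 77% at 40% hard, and 69%, 94% and 96% at 80% hard.

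**5. Splitting the loss.** At 40% hard, replacing raw change by a percentage gains 47 − 18 = 29 points, and restricting to hard segments gains a further 76 − 47 = 29. At 50% hard the two steps are 59 − 28 = 31 and 82 − 59 = 23. Adjusting raw change for the number of affected segments gives 54% at 40% hard with no typing at all. About half of the loss is therefore a matter of baseline adjustment.

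**6. Power when easy segments also benefit** (same model, 40% hard).

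| Easy clearance | Hard clearance | % of all cleared | % of hard cleared |
|---|---|---|---|
| 88% → 92% | 40% → 60% | 75% | 78% |
| 80% → 90% | 40% → 60% | 93% | 78% |
| 85% → 92% | 40% → 52% | 63% | 38% |
| 80% → 90% | 40% → 50% | 67% | 27% |

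In the first two rows raw change has 23% and 40%.

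**7. Graded score instead of cleared or not** (40% hard). With no easy-segment effect, power is 44% for whole-score percent reduction and 74% for the hard-only version. With easy clearance rising from 80% to 90% it is 91% and 75%. Raw change has 13% and 40% in these two cases, against 44–48% and 91–92% for percent or baseline-adjusted change of the whole score.

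**The case against.** The strongest reply is that the score is undefined. The words about scoring each patient introduce the correlation with haemodynamics and do not define the Section 5 outcome. Objective 2 says that a scoring method is still to be established, so weights or sub-scores by segment type are not ruled out, and the research-process figure is missing from the text available. This stands. A reader might infer that the plan commits to one whole-patient sum. The documents do not say so; they only fail to say how the type is used.

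Second, no passage states that the conventional operation clears easy segments equally well in both arms. Section 1 describes positioning and complete removal of the embolism generally, and the worked example in Section 4 describes stripping in each segment. This also stands, and step 6 shows that it matters: a modest gain in easy segments makes the whole score the more powerful measure.

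Third, the CT score is one of several secondary outcomes and the trial is sized on mean PAP. That is correct and limits the importance of the point.

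What the reply does not remove is that the type is recorded and unused in the readable text, and that an unadjusted raw change was the weakest measure of the whole score, with or without an effect in easy segments.

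**Conclusion.** The point holds in a limited form. The readable plan types segments and uses the type in no endpoint or analysis, and its clearance outcome has no baseline adjustment. If the benefit lies mainly in hard-to-reach segments, a whole-patient change dilutes it. With 40% of segments hard and no effect in easy ones, power is roughly 15–18% for raw change, about 50% for a percentage of all segments and 76–79% for hard segments only. These figures depend on assumed shares and clearance rates.

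Two stronger conclusions are tempting and are not supported. One is that a hard-only score should replace the whole score; that depends on easy segments not benefiting, which the documents do not state. The other is that a null CT result could be put down to dilution; the size of any dilution cannot be computed from the documents. The case for relating the change to baseline is firmer, since it does not depend on where the benefit lies. The primary mean PAP calculation is unaffected.

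**What to change.** In Sections 5 and 6:

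- Define the CT score. Keep the whole-patient score, but compare arms relative to baseline, by ANCOVA on the baseline score or by percent reduction.
- Pre-specify beside it, as a secondary result, the per-patient reduction over segments typed ii or iii. Adjust this for baseline too, because type iii segments have small baseline scores and simple percentages would be unstable. Show type i as supporting.
- Keep one value per patient. Do not pool segments as if they were independent.
- Type segments from the stored pre-operative CT by one written rule in both arms. Section 4 states the precise CT analysis for the precise therapy group, so control-arm typing needs to be stated explicitly. Section 7 already has at least two staff assess the imaging; mask those readers to arm, and do not pass control-arm typing to the surgeon.

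Cost: SAP wording, one derived variable, one more secondary comparison, and possibly a reading of stored control-arm scans. Patients with no hard-to-reach segment do not contribute to that one result (about 2% at 40% hard and 7% at 25% hard in the simulation), and the SAP should state this against its intention-to-treat rule. No new patients or examinations are needed.
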